2.0 Background

2.1 Prior experience and gaps in current knowledge.

Smoking causes multiple types of cancer, including cancers of the oral cavity and pharynx, larynx, esophagus, lung, stomach, kidney, pancreas, liver, bladder, cervix, colon and rectum, and acute myeloid leukemia (American Cancer Society (ACS), 2021, US Department of Health and Human Services (USDHHS), 2014). Further, patients who smoke at the time of their cancer diagnosis have an increased risk of cancer recurrence, treatment complications, and mortality due to cancer-related and all-cause mortality (USDHHS 2014; National Cancer Institute (NCI), 2022). Moreover, evidence is accumulating that smoking cessation after diagnosis is associated with significantly reduced all-cause mortality (USDHHS, 2014; NCI, 2022).

While smoking is clearly related to increased risk negative health outcomes amongst cancer patients, it is also clear that patients with cancer far too rarely receive treatment for their smoking as part of their cancer care (Cooley et al., 2018; Croyle et al. 2019; Day et al., 2019; Peters et al. 2012). Research suggests that rates of undertreatment may be related to cancer care clinicians' beliefs that they are too busy to intervene with smoking or that they are not adequately prepared to treat their patients' smoking (Price et al. 2019).

Unfortunately, we currently know far too little about how to best help cancer patients quit smoking. This knowledge gap reflects a lack of rigorous trials of smoking cessation interventions for cancer patients (NCI, 2022). As such, at present the evidence is mixed as to whether smoking cessation pharmacotherapy and counseling significantly improve smoking cessation rates in cancer patients (NCI, 2022). There are reasons to suspect that treatments that effectively promote smoking cessation in general adult populations may be less effective in patients with cancer (e.g., those who continue smoking after a cancer diagnosis may be especially dependent on nicotine, the stress of cancer or its treatment may be a potent trigger to smoking lapses or relapses, patients may lack the energy or time to complete smoking cessation treatment in the midst of cancer treatment; fatalism may undermine motivation to quit). As such, it is important to identify treatments that are effective in promoting smoking cessation among cancer patients, and in the context of cancer care.

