3.2 Primary & Exploratory Aims

Primary Aims

Aim 1: To establish the feasibility of the CET protocol and procedures in preparation for a full-scale future trial.

Aim 2: To generate estimates of the size of the comparative effects of intensive, cancer-specific smoking cessation treatment versus a generic, lower-

PROTOCOL TITLE: Comparative Effectiveness Trial of Tobacco Cessation Treatments among Cancer Patients who Smoke

intensity recommended smoking cessation treatment in terms of biochemically confirmed 7-day point prevalence abstinence (no smoking in the past 7 days) 26 weeks after a target quit date.

Exploratory Aims

Aim 3: To estimate differences in CET arms in exploratory outcomes including patient acceptability, completion, adherence, costs, and cost-effectiveness.

Aim 4. To elicit input from patients who have experienced cancer to inform study methods and interventions.

Aim 5. To estimate the extent to which treatment effects on abstinence and exploratory outcomes differ across patient subpopulations based on demographics (age, race, sex, ethnicity, socioeconomic disadvantage); nicotine dependence; and cancer site, stage, and treatment phase.

Aim 4. To explore relations between 1) engagement in tobacco treatment and 2) quitting smoking and health and healthcare utilization outcomes, including cancer outcomes overall, and as a function of environmental exposures and, for those enrolled in the CET, randomly assigned treatment condition.

3.3 Study hypotheses.

The primary hypothesis to be tested for Aim 1 is that at least 12% of eligible adult patients who have cancer and smoke cigarettes and are referred to the tobacco treatment outreach team will initiate an evidence-based form of smoking treatment (either Wisconsin Tobacco Quit Line care or treatment offered in the CET).

The primary hypothesis to be tested for Aim 2 is that more-intensive, cancer-specific smoking cessation treatment will increase the log odds of achieving 7-day abstinence 26 weeks after a target quit date by at least 50% over the comparator condition (predicted odds ratio ≥ 1.50).

Exploratory hypotheses include the following:

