4.3 **Criteria for considering participants “enrolled.”** Individuals will be considered enrolled in the study at the point of randomization to a study arm in the CET. Randomization will occur after oral consent to participate and completion of baseline assessments. People who do not complete oral consent and randomization will not be considered fully enrolled and will be replaced until 50 people are randomized in the CET (25 in each arm).

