PROTOCOL TITLE: Comparative Effectiveness Trial of Tobacco Cessation Treatments among Cancer Patients who Smoke

the application). The interview will address the participants' cancer experiences, tobacco use history, smoking and supportive care outreach, and smoking treatment. The interview outline is uploaded with the application. These interviews will be recorded and transcribed without participant identifying information.

Oral consent. In the oral consent process, UW-CTRI study coordinators will read the oral informed consent script to participants and will then ask if they have any questions. The study coordinator will answer questions during the call, or will schedule a follow-up call if the patient needs more time to make a decision about the study or if the study coordinator needs to consult with the PI or other team member to address the patient's concerns or questions. Once the patient's questions have been fully addressed, the patient will be asked questions to assess their comprehension of key CET study features. People who are unable to answer these questions correctly, even after review of key points by the study coordinator, will be considered unable to consent and will be referred to their care team and given information about WTQL services. Those who pass the comprehension screening will be asked if they consent to participate in the CET study.

Baseline assessment. Next, participants will complete a baseline assessment (see uploaded survey) of their tobacco use history, nicotine dependence, quitting motivation, quitting confidence, stress, mood, wellbeing, quality of life, support system, symptom burden, and demographics. Participants will also select a target date to quit smoking within the next 60 days at this call. These activities will occur during the enrollment phone call if participants are willing and able to stay on the call. If they are not, the UW-CTRI study coordinator will schedule this assessment call within the following 1-2 weeks.

Randomization. Participants will next be randomized to treatment. Participants will be considered fully enrolled once consented, baseline assessment is complete, and randomized. Study coordinators and participants will be informed of the randomly assigned condition after the baseline assessment is completed.

Treatment procedures. These are described in section 13.1 above.

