We will examine reach of the treatment by computing the proportion of all participants meeting inclusion criteria for proactive tobacco outreach who were referred to WTQL, referred to their PCP, and the proportion who were screened for, eligible for, and enrolled/randomized in the CET. As such, the pool of participants for Aim 1 includes everyone eligible for inclusion on at least 1 CRDS report that guides proactive tobacco treatment outreach. The pool of participants included in Aims 2, 3 and 5 will comprise all participants who were randomized to treatment in the CET. The pool for Aim 4 will include all participants who participated in a qualitative interview.

20.4 Statistical Methods.

Descriptive statistics will be used to characterize smoking treatment reach (the proportion of eligible patients who initiate any smoking cessation treatment, and the proportion who enroll in the CET. These rates will be computed overall, and by patient subpopulation.

Logistic regression will be used to estimate the effects of treatment condition on binary outcome data (e.g., abstinence, side effects), overall and by patient subgroups (i.e., moderation effects). Odds ratios and numbers needed to treat will be computed to estimate treatment effect sizes.

Analyses of variance will be used to examine condition effects on continuous variables such as ratings of treatment satisfaction, burden, and treatment effects on ratings of patient experiences and candidate treatment mediators (e.g., withdrawal). Treatment effect sizes will be computed. Cost-effectiveness will be calculated based on the incremental cost-effectiveness

PROTOCOL TITLE: Comparative Effectiveness Trial of Tobacco Cessation Treatments among Cancer Patients who Smoke

ratio of enhanced treatment versus standard treatment per each additional case of abstinence.

Thematic analysis of qualitative interview will identify themes that emerge in patient interviews in the following areas: cancer experiences, supportive care outreach, tobacco history, and tobacco treatment.

20.5 Planned Interim Analysis.

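### No baseline covariate is named for the overall abstinence effect, so a chance imbalance in nicotine dependence would stay in the pilot's effect size; one supportive adjusted estimate would address this

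*Combined protocol and SAP*

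**What the plan says.** Section 20.4 gives the model for abstinence: "Logistic regression will be used to estimate the effects of treatment condition on binary outcome data". The sentence goes on to cover "binary outcome data (e.g., abstinence, side effects), overall and by patient subgroups (i.e., moderation effects", so subgroup models are planned as well. No baseline covariate is named for the overall effect there, and sections 20.2 and 20.6 add none. The plan does not say that covariates are excluded.

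On allocation, section 4.3 says that people who do not complete consent and randomisation "will be replaced until 50 people are randomized in the CET (25 in each arm"). Section 13.1 says only "Participants will next be randomized to treatment". Stratification, blocking and minimisation are not mentioned.

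On dependence, section 13.1 places it in the pre-randomisation "baseline assessment (see uploaded survey) of their tobacco use history, nicotine dependence, quitting motivation, quitting confidence", and the schedule in section 13.2 lists it at enrolment. Its planned role in the treatment-effect analyses is in exploratory Aim 5 (section 3.2), where effects are to be estimated across groups defined by factors including "socioeconomic disadvantage); nicotine dependence; and cancer site, stage, and treatment phase".

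Section 20.2 explains that 50 participants were chosen to obtain stable effect estimates for designing a full-scale trial. It concedes that this is too few to test moderate benefits sensitively.

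**The concern.** The main product of this pilot is an effect size, and it will come from a single randomisation of 50 people. With 25 per arm, the arms can easily differ by chance on a baseline factor that predicts quitting. Dependence is a plausible factor of this kind. Section 2.1, listing reasons why treatments may work less well in cancer patients, remarks that "those who continue smoking after a cancer diagnosis may be especially dependent on nicotine".

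If the enhanced arm happens to receive the more dependent smokers, the unadjusted odds ratio comes out too low for that sample; in the reverse case it comes out too high. As written, nothing in the overall analysis would correct this or show how much of the estimate it explains. Because the plan is silent, a choice to adjust could also be made after the outcomes are known.

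**Working it through.** **Inputs from the documents.** 25 per arm (section 4.3). Predicted odds ratio 1.50 (sections 3.3 and 20.1). Abstinence of 34.5% against 21.5% in a cited trial of intensive treatment in cancer patients (section 2.5). An odds ratio of 2.94 in an earlier primary care trial (section 2.4).

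**Assumptions.** The documents give no control rate for this trial and no figure for how strongly dependence predicts abstinence. The control rate is taken as 21.5%, with 12% as a low case. The base case for dependence is 1.65-fold lower odds per SD, with a range from 1.0 (no prognostic value) to 2.5. The sample size of 50 is stated without a calculation, so there is no plan figure to reproduce.

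**Step 1: size of chance imbalance.** Under simple randomisation the standardised difference d between arms has SD √(2/25) = 0.283. Hence P(|d| > 0.3) = 29% and P(|d| > 0.5) = 7.7%.

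**Step 2: effect on the odds ratio.** To a first approximation the unadjusted odds ratio is multiplied or divided by exp(|d| × ln OR per SD). With ln 1.65 = 0.50:

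- 1-SD imbalance (d = 0.283): exp(0.283 × 0.50) = 1.15
- 1.96-SD imbalance (d = 0.554): exp(1.96 × 0.283 × 0.50) = 1.32

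On the log scale these are 0.1416 / 0.4055 = 35% and 0.277 / 0.4055 = 68% of ln 1.50. Other assumed strengths give:

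| OR per SD | d = 0.3 | d = 0.5 |
|---|---|---|
| 1.25 | 1.07 | 1.12 |
| 1.5 | 1.13 | 1.22 |
| 2.0 | 1.23 | 1.41 |
| 2.5 | 1.32 | 1.58 |

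**Step 3: comparison with sampling error.** At 21.5% control and an odds ratio of 1.50 (29.1% in the enhanced arm), SE(log OR) = 0.656. The 95% interval is 1.50 × exp(±1.96 × 0.656) = 0.41 to 5.43. A 1-SD imbalance contributes about (0.1416 / 0.656)² = 4.7% of that variance. Imbalance is therefore a small part of total uncertainty, and the interval already includes it.

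**Step 4: does adjustment remove the imbalance?** In simulation (3,000 trials per scenario, 21.5% against 34.5% or 29.1%, 1.65 per SD), the unadjusted log odds ratio moved by −0.42 to −0.52 per unit of d. With a one-covariate Firth model and standardised risks it moved by +0.06 to −0.05. The imbalance component is essentially removed.

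**Step 5: precision gain.** The comparison must be Firth with Firth. With arm alone and 25 per arm, Firth estimates each risk as (y + 0.5)/26. The risk difference shrinks by 25/26 and its variance by 1 − (25/26)² = 7.5%, with no covariate at all. Like for like (3,000 trials, 34.5% against 21.5%), the variance ratios for the risk difference were 1.01, 0.98, 0.96 and 0.93 at 1.0, 1.35, 1.65 and 2.0 per SD. The covariate's own gain is thus about 0–2% at 1.35, 4% at 1.65 and 7% at 2.0. At a 12% control rate there is no gain, or a slight loss, unless the covariate is strong.

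**Step 6: validity and power.** In 2,000 trials per scenario at 21.5% control, rejection under the null was 2.9–4.1% unadjusted and 3.2–3.7% adjusted (two-sided 5% Wald test, ordinary logistic fit). The median unadjusted log odds ratio under the null was 0.00. Adjustment changed power by about 3 points at most (41.9% to 45.3% at odds ratio 2.94 and 2.5 per SD).

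**Step 7: number of covariates.** Expected abstainers are 25 × 0.345 + 25 × 0.215 = 14. At a 10% control rate and odds ratio 1.50 there would be about 6. One covariate is the prudent limit.

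**The case against.** The strongest reply is that nothing here is invalid. Randomisation protects the unadjusted comparison, type I error is controlled, and the interval of roughly 0.41 to 5.43 dwarfs any plausible imbalance. The plan itself says the sample is too small for moderate effects. All of this stands, and it limits the point to a minor one.

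It can also be said that the plan does use dependence in treatment-effect models. That is correct. A reader might infer that dependence is ignored, but Aim 5 and the moderation clause in section 20.4 do not support that reading. Those models are exploratory and do not supply the headline estimate. Likewise, an unadjusted overall model is an inference from silence, not something the plan declares.

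A third reply is that dependence is only one of several baseline candidates, since motivation and confidence are also measured, and that its prognostic strength is unknown. This stands too. A reader might take dependence to be an established strong predictor here, but section 2.1 offers only a qualitative remark. Dependence is a reasonable single choice because it is collected before randomisation and already named in Aim 5. The documents do not show that it is the best one.

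Finally, adjustment can widen the log odds ratio: with an ordinary fit its SD rose from 0.72 to 0.80 (odds ratio 1.50, 2.0 per SD). Part of that arises because the conditional odds ratio is a different, larger quantity. Standardising back to a marginal effect avoids this mismatch, so the objection does not apply to the form proposed under the fix.

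**Conclusion.** The point holds as a low-cost improvement, not as a flaw in validity. A realised imbalance in dependence would be left in the effect size that is to inform the full-scale trial. Under the assumed 1.65-fold effect per SD, a typical (1-SD) imbalance moves the odds ratio by a factor of about 1.15 and a 1.96-SD imbalance by about 1.32, against a predicted 1.50. If dependence is a weak predictor the shift is minor.

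Two stronger conclusions should not be drawn. First, ordinary imbalance does not rival the predicted effect: a 1-SD imbalance is about a third of ln 1.50, and the 1.96-SD case about two thirds. Second, adjustment does not buy much precision. Setting a Firth-adjusted estimate against an ordinary unadjusted one suggests 8–13% lower variance, but most of that is penalty shrinkage and the figure should not be used. The like-for-like gain is about 0–2%, 4% and 7% at 1.35, 1.65 and 2.0 per SD with a 21.5% control rate, and nil or slightly negative at 12% unless the covariate is strong.

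The conclusion rests on simple randomisation, the assumed prognostic strength and the assumed control rates.

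**What to change.** In section 20.4, state that the unadjusted estimate is primary, and pre-specify one supportive estimate of the overall abstinence effect:

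- Firth logistic regression on arm plus the continuous enrolment dependence score, with no other covariate.
- Results standardised over the randomised sample to a marginal risk difference and marginal odds ratio, each with a bootstrap 95% CI, reported beside the unadjusted result.

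The penalty keeps the fit finite when an arm has no abstainers; at a 12% control rate about 4–8% of simulated trials had an arm in which none or all were abstinent. Justify the analysis as a correction for the realised imbalance, not as a gain in power. Section 13.1 should also say whether randomisation is stratified.

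The cost is a few sentences and one extra model with a bootstrap. No new data are needed, and the planned unadjusted result is still reported.

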2.3 Exploratory Aims

Exploratory aims of the pilot CET are:

3. To estimate differences in CET arms in exploratory outcomes including patient acceptability, completion, adherence, costs, and cost-effectiveness.
4. To elicit input from patients who have experienced cancer to inform study methods and interventions.
5. To estimate the extent to which treatment effects on abstinence and exploratory outcomes differ across patient subpopulations based on demographics (age, race, sex, ethnicity, socioeconomic disadvantage); nicotine dependence; and cancer site, stage, and treatment phase.
6. To explore relations between 1) engagement in tobacco treatment and 2) quitting smoking and health and healthcare utilization outcomes, including cancer outcomes overall, and as a function of environmental exposures and, for those enrolled in the CET, randomly assigned treatment condition.

2.4 Preliminary data.

The opt-out referral model to be adapted in this project has increased the reach of smoking cessation treatment in primary care and inpatient contexts (Creswell et al., 2022; [name] et al., 2022). In this approach, referral to or connection with treatment is the default for all adults whose EHR records suggest they currently smoke, unless a patient actively opts out of such referral. We are currently employing a similar opt-out referral

PROTOCOL TITLE: Comparative Effectiveness Trial of Tobacco Cessation Treatments among Cancer Patients who Smoke

approach in 22 clinics in 2 health systems (UW IRB Protocol #: 2019-0054, 2019-0939, 2022-0124, and especially 2022-0973) with great success. Over the past 2.75 years, this referral strategy has led to the enrollment of more than 1300 adult patients who smoke in smoking treatment trials. All of these protocols involve mailing patients who meet initial eligibility prerequisites based on information in their EHR a study launch letter that offers them an opportunity to opt out of study recruitment, and then proactive telephone outreach to patients who have not opted out of such contact to offer both standard tobacco treatment and the opportunity to enroll in a tobacco treatment trial.

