Despite compelling evidence that smoking increases risks for negative outcomes, many patients with cancer continue to smoke after diagnosis, and cessation treatment is not consistently integrated into cancer care, particularly for minoritized groups (Cooley et al., 2018; Croyle et al., 2019; Ramaswamy et al., 2016; D'Angelo et al., 2021). Research suggests that while many patients with cancer are advised to stop smoking, fewer than half of cancer patients receive treatment to help them do so (Borger et al., 2022; Price et al., 2019). Importantly, evidence shows that many cancer patients are interested in trying to quit and the majority of cancer patients try to quit following their diagnosis (Gritz et al., 2020). However, such quit attempts are very often unsuccessful with at least half of patients with cancer continuing to smoke after diagnosis (Gritz et al., 2020; Sharp et al., 2014). Even with strong motivation to quit, only half of head and neck cancer patients in a recent study abstained from smoking for at least 24 hours, and only 10% were able to quit for at least 30 days (Borger et al., 2022).

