The cancer-focused smoking cessation counseling protocol that will be used in the intensive treatment will be based on the counseling used in the recent randomized controlled trial conducted by Park and colleagues (Park et al., 2020), and informed by the qualitative interviews completed with patients in the qualitative substudy. The Park et al. study was conducted in patients with a variety of cancer diagnoses and showed that such intensive treatment produced higher smoking abstinence rates at 6 months post-treatment than did a less intense treatment (34.5% vs. 21.5%). However, few studies of smoking treatment in cancer patients have manipulated pharmacotherapy intensity, and results to date have been inconclusive (Schnoll et al., 2010, 2019). In addition, the Park et al., (2020) did not systematically vary pharmacotherapy treatment across the two experimental conditions; thus, it may underestimate the effectiveness of more intensive treatment.

In addition to addressing a novel research question, the research methods for the CET are also innovative in their integration of patient self-report data on treatment utilization, acceptability, burden, tolerability, adherence, and success (in terms of abstinence rates) with treatment cost data and EHR-extracted data on healthcare utilization, complications, and clinical outcomes to facilitate a multi-dimensional comparison of the 2 treatment conditions (i.e., a comparison of treatment not just in terms of abstinence, but also in terms of likely population impact and efficiency). This work is much needed given the dearth of rigorous trials of smoking treatments in this high-priority population.

We anticipate that the proposed feasibility pilot test will demonstrate that automatic, opt-out referral of cancer patients who smoke to centralized, low-barrier smoking cessation treatment resources is feasible. We anticipate that at least 12% of patients eligible for referral will enter evidence-based smoking treatment, the rate we observe in primary care settings. We also anticipate that

PROTOCOL TITLE: Comparative Effectiveness Trial of Tobacco Cessation Treatments among Cancer Patients who Smoke

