4. Differences in rates of treatment reach, retention, and completion by patient factors (demographics, nicotine dependence, smoking history). (Aim 5).
5. Moderation of treatment effects (high- vs. low-intensity) by patient factors. (Aim 5).

PROTOCOL TITLE: Comparative Effectiveness Trial of Tobacco Cessation Treatments among Cancer Patients who Smoke

6. Health outcomes (e.g., cancer mortality, cancer progression, new cancer diagnoses, treatment side effects).

3.5 Primary safety endpoints.

1. Adverse events, by treatment condition.
2. Serious adverse events, by treatment condition.

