20.0 Study Analysis

20.1 Statistical Hypotheses.

The primary hypothesis to be tested for Aim 1 is that at least 12% of eligible adult patients who have cancer and smoke cigarettes and are referred to the tobacco treatment outreach team will initiate an

PROTOCOL TITLE: Comparative Effectiveness Trial of Tobacco Cessation Treatments among Cancer Patients who Smoke

evidence-based form of smoking treatment (either Wisconsin Tobacco Quit Line care or treatment offered in the CET).

The primary hypothesis to be tested for Aim 2 is that more-intensive, cancer-specific smoking cessation treatment will increase the log odds of achieving 7-day abstinence 6 months after a target quit date by at least 50% over the comparator condition (predicted odds ratio ≥ 1.50 in this superiority comparison).

Secondary hypotheses include the following:

For Aim 3, we hypothesize that the majority ($\geq 50\%$) of patients assigned to each condition will initiate treatment and will receive at least some counseling and use at least some of the provided medication. We expect retention, adherence, and satisfaction with treatment to be higher in the enhanced treatment relative to standard care. We anticipate that the more intensive, enhanced treatment, although more costly, will be cost-effective in terms of the incremental cost effectiveness ratio per additional patient who quits smoking, relative to the comparator condition and to other preventive health interventions. For these superiority hypotheses, the null hypotheses are that the two treatments are equally acceptable and efficient.

For Aim 4, we expect to elicit information that will help us better communicate with and support patients eligible for tobacco treatment outreach and CET counseling by learning more about the experiences and perspectives of people who have had cancer.

For Aim 5, we expect treatment reach to be especially high among historically undertreated populations (including African-American, Medicaid-eligible patients, and those from disadvantaged neighborhoods), and for the effects of enhanced treatment (vs. standard care) to be similar across patient subgroups. Thus, we are anticipating superior reach in historically underserved patient groups, and equivalent effectiveness across patient groups.

20.2 Sample Size Justification.

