In this pilot study, we seek to demonstrate the feasibility and acceptability of the proactive outreach model as a way to enhance the reach of smoking treatment, and as a feasible way to recruit participants for a CET of enhanced vs. standard smoking cessation treatment. We also hope to generate estimates of enhanced vs. standard treatment effects on biochemically verified 7-day point-prevalence abstinence rates 6 months after a target quit date (primary outcome) and other abstinence measures (e.g., self-reported prolonged and point-prevalence abstinence 3 and 6 months post-quit). As such, we selected a sample size of 50 to generate stable estimates of the size of treatment effects on these outcomes and costs,

PROTOCOL TITLE: Comparative Effectiveness Trial of Tobacco Cessation Treatments among Cancer Patients who Smoke

and to permit exploration of differences in treatment effects by sex, race, ethnicity, and disadvantage. A sample of 50, while too small to sensitively test for moderate treatment benefits, is sufficient to pilot test all study and treatment procedures and to yield informative effect estimates that will guide a future, full-scale CET of standard and enhanced care.

The primary outcome will be analyzed in an intent-to-treat analysis in which all randomized participants are included, and missing cases are assumed to be non-abstinent. This will be supplemented by sensitivity analyses that again use the full sample of randomized participants to examine robustness of results across different assumptions regarding missingness. Multiple imputation will not be used in this pilot project.

For the qualitative study, we will recruit as many participants as we can until we reach thematic saturation in qualitative data coding. We anticipate that this will occur with fewer than 32 participants.

20.3 Participant Population(s) for Analysis.

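### The planned logistic subgroup models for abstinence have no sparse-cell method, so with 25 per arm the interaction odds ratio will often not be finite for small subgroups and many-level factors

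*Combined protocol and SAP*

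**What the plan says.** Section 20.4 applies logistic regression to binary outcomes, abstinence among them, "overall and by patient subgroups (i.e., moderation effects", and expresses effects as odds ratios and numbers needed to treat. Aim 5 (sections 2.3 and 3.2) names nine factors: "demographics (age, race, sex, ethnicity, socioeconomic disadvantage); nicotine dependence; and cancer site, stage, and treatment phase". Section 3.4 lists as an exploratory endpoint "Moderation of treatment effects (high- vs. low-intensity) by patient factors".

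Section 4.3 fixes the sample: people who do not complete consent and randomization "will be replaced until 50 people are randomized in the CET (25 in each arm". Section 20.2 says that 50 was chosen to give stable effect estimates and "to permit exploration of differences in treatment effects by sex, race, ethnicity, and disadvantage", which covers four of the nine factors. It also concedes that 50 is too few to test moderate benefits sensitively.

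The plan does not say how factors will be coded or levels collapsed, what cell size is the minimum, or what will be done if a model fails to converge. No penalised or exact estimator is named.

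**The concern.** A treatment-by-factor logistic model estimates the log odds of abstinence in every arm-by-level cell. If a cell is empty, or everyone in it smokes, or everyone in it is abstinent, ordinary maximum likelihood has no finite estimate for that cell or for any interaction that uses it. Software commonly returns a very large coefficient with a very large standard error.

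Two things are at stake. The pilot is meant to supply effect estimates for a full-scale trial, and an odds ratio that runs to infinity supplies none. Also, section 20.1 expects similar effects across patient groups. A separated model typically gives a non-significant Wald test, which could be misread as support for that expectation.

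**Working it through.** **Inputs**
- 25 per arm: section 4.3.
- Abstinence rates: section 2.5 describes a cited trial in cancer patients where intensive treatment gave higher abstinence "than did a less intense treatment (34.5% vs. 21.5" (percentages). The plan does not adopt these as planning values; using them is an assumption.
- Low-rate reference: section 2.5, a cited head and neck cancer study where "only 10% were able to quit for at least 30 days". This is a different outcome, used only to set a lower range.
- Hypothesized effect: section 20.1, "predicted odds ratio ≥ 1.50 in this superiority comparison".
- Subgroup prevalences and numbers of levels: not in the documents, so a range is assumed.

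**Step 1. The plan's own figure.** Section 20.2 gives no formula, assumed rate or precision target behind 50, so there is nothing to reproduce.

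**Step 2. Expected abstinent participants**
- Cited rates: 25 × 0.345 + 25 × 0.215 = 8.6 + 5.4 = 14.0.
- 21.5% with an odds ratio of 1.5: the enhanced rate is 29.1%, and 25 × (0.215 + 0.291) = 12.7.
- 10% with an odds ratio of 1.5: odds 0.1111 × 1.5 = 0.1667, so the enhanced rate is 14.3%, and 25 × (0.100 + 0.143) = 6.1.

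Section 20.6 codes unverified cases as smoking, which tends to lower these counts.

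**Step 3. One subgroup of fixed size n per arm.** P(at least one all-smoking or all-abstinent cell) = 1 − Π over arms of [1 − pⁿ − (1−p)ⁿ], at the cited rates.
- n = 5: 1 − (0.701 × 0.875) = 0.39.
- n = 3: 1 − (0.506 × 0.678) = 0.66.

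**Step 4. Binary factor with prevalence q, subgroup size random.** In each arm the subgroup size m is Binomial(25, q). The probability that both levels of that arm are usable is

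A(q, p) = Σ (m = 1 to 24) C(25, m) qᵐ(1−q)²⁵⁻ᵐ [1 − pᵐ − (1−p)ᵐ] [1 − p²⁵⁻ᵐ − (1−p)²⁵⁻ᵐ].

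P(no finite interaction odds ratio) = 1 − A(q, p control) × A(q, p enhanced). Exact enumeration gives:

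| Prevalence q | 34.5% vs 21.5% | 29.1% vs 21.5% | 14.3% vs 10% |
|---|---|---|---|
| 50% | 0.130 | 0.149 | 0.634 |
| 30% | 0.260 | 0.290 | 0.729 |
| 20% | 0.476 | 0.508 | 0.835 |
| 10% | 0.830 | 0.844 | 0.954 |
| 5% | 0.972 | 0.974 | 0.993 |

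Cells with no participants at all are uncommon except in rare subgroups (0.138 at 10% prevalence, 0.478 at 5%). Cells with no abstinent participant cause most failures.

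**Step 5. Factors with several equal levels** (40,000 simulated trials; failure means at least one bad cell). At the cited rates: 0.495 for three levels, 0.825 for four, 0.970 for five. At 14.3% vs 10%: 0.938, 0.996 and 1.000.

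**Step 6. Continuous factors.** With a normally distributed moderator, complete separation within an arm occurred in 0.4% of simulated trials at about 14 events and in 11% at about 6.

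**Step 7. Precision when the estimate is finite.** For a 50:50 factor at the cited rates, with 12.5 expected per cell, SE(log interaction odds ratio) = √[2/(12.5 × 0.215 × 0.785) + 2/(12.5 × 0.345 × 0.655)] = √(0.948 + 0.708) = 1.29. The 95% interval extends by a factor of exp(1.96 × 1.287) ≈ 12.5 either way.

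**The case against.** The strongest reply is that the plan has already discounted this analysis. Aim 5 and the moderation endpoint are labelled exploratory, section 20.2 admits the sample is small, and section 3.1 says the endpoints serve to estimate effects for a later trial. An infinite odds ratio is also easy to see in the output. This stands as far as severity goes: no decision rule depends on these models. It does not remove the gap, because low power and the absence of a finite estimate are different problems, and the plan concedes only the first.

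Three stronger readings are tempting, and the documents do not support them.
- A reader might infer that the plan prescribes a wrong estimator. Section 20.4 says only logistic regression. Unqualified, that ordinarily means maximum likelihood, but penalised and exact versions are not excluded. The defect is an unspecified method for sparse data.
- A reader might infer that all nine factors fail, or that section 20.2 claims the sample supports all nine. Section 20.2 names four. Sex may well be near balance, and age and dependence can stay continuous.
- A reader might infer that the equity question as a whole fails. Equity also covers treatment reach by subgroup, which section 20.4 handles descriptively among the roughly 833 patients to be approached (section 4.2). That strand does not use these models.

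**Conclusion.** The concern holds for small subgroups and many-level factors. At the cited abstinence rates, the interaction odds ratio for a binary factor is not finite in about 13% of trials at 50% prevalence, rising to 83% at 10% and 97% at 5%. A factor with four equal levels fails in about 83%. If abstinence is nearer 14% and 10%, a balanced factor fails in about 63%.

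These sizes rest on rates borrowed from cited studies and on assumed prevalences and level counts. Which factors are affected is therefore a judgement; race, ethnicity, cancer site and stage are the plausible ones. The point concerns the method and reporting of an exploratory aim, should be put right before analysis, and leaves the primary abstinence comparison untouched.

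**What to change.** In section 20.4:
- Make the main subgroup report the number abstinent over the number randomized, by arm and level, with the risk difference and a score-based 95% interval. This extends the absolute measure already planned (number needed to treat).
- Where an odds ratio or interaction is reported, use Firth penalised logistic regression with profile-likelihood intervals.
- Keep age and nicotine dependence continuous.
- Report descriptively only any factor with a sparse level, and define sparse in advance. A cutoff of 5 per arm is not enough by itself, since such a subgroup still has a 39% chance of an all-smoking or all-abstinent cell.

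In section 20.2, restate that the sample permits only descriptive exploration by race, ethnicity and other small subgroups.

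The cost is small: no new data or participants, and standard software. The downsides are mild shrinkage of odds ratios toward 1 and fewer modelled interactions. Firth makes the estimates finite, not precise, so the wide intervals should be shown beside every subgroup odds ratio.
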